11.2.1. Enrollment Limits

Group A: Group A consists of 2 sites. Each site may enroll no greater than 70% of Group A subjects.

Group B: Group B consists of up to 9 sites. Each site may enroll no greater than 30% of Group B subjects.

11.3. Primary Endpoint Rationale

Group A: Anesthesia Effectiveness (Subject-Reported)

In Group A, active lidocaine iontophoresis will be compared to sham lidocaine iontophoresis (ie, lidocaine in the ear canal but without activating the iontophoresis unit for that channel). After iontophoresis/sham treatment is complete, the subject will use the VAS to rate the pain associated with a single tympanic membrane tap using a standardized blunt otologic probe. The VAS was selected because it is a validated self-report pain instrument commonly used in research settings with adults (reviewed in Jensen and Karoly).³⁴ The VAS is validated for use in subjects 8 years of age and older (reviewed in Stinson et al (2006)).³⁵ The VAS consists of a 10 centimeter (cm) line with a statement at each end representing the extreme limits of pain intensity (“No pain” to “Worst possible pain”). The subject reports their pain intensity by making a mark along the line and the line is measured to convert the subject response to numeric score (0-10 in centimeters).

[REDACTED]

[REDACTED]

[REDACTED]

Group B: Tube Placement Tolerability

The goal of Group B is to demonstrate that the pain associated with tube insertion using the TDS after lidocaine iontophoresis provided by the IPS will be tolerable for pediatric subjects. [REDACTED]

[REDACTED] In Group B, ears indicated for tympanostomy tubes will receive active lidocaine iontophoresis and tympanostomy tube insertion using the TDS, and the pain associated with tube insertion will be collected using the VAS. The mean VAS score will be compared to a performance goal (PG).

[REDACTED]

[REDACTED]

[REDACTED]

[REDACTED] Jensen et al (2003) re-analyzed 2 randomized controlled trials of postoperative pain for adults using VAS (N=123 and N=125).³⁹ They determined

cut points for pain severity as no pain at 0 to 4 mm, mild pain 5 to 44 mm, moderate pain 45 to 74 mm and severe pain 75 to 100mm. Altogether, the literature reports show remarkable consistency for the experimentally-determined cut point between mild and moderate pain.

Prior TULA in office tube delivery study results indicate that tolerability scores are anticipated to be in the mild range. Therefore, it is reasonable to set a performance goal to be superior to (less painful than) moderate pain. Using the VAS, Tusker will demonstrate superiority to a score of 4.5cm (or 45mm), based on Jensen's determined cut point of 45mm for adult VAS scores, showing that the pain associated with in-office tube insertion in adult subjects is mild.

11.4. Study Population

Group A will consist of 40 healthy adult volunteers and Group B will consist of 30 adults indicated for tympanostomy tubes in one or both ears. The study may enroll up to 85 subjects to achieve 40 subjects with evaluable data in Group A and 30 subjects with evaluable data in Group B, allowing for approximately 15 screen failure or withdrawn subjects.

11.4.1. Definition of Enrollment

All subjects who consent for participation in the study are considered enrolled. Subjects who do not meet eligibility criteria are considered screen failures. **Section 14.0** Statistical Methods provides further definition of subjects included in the analysis sets.

11.5. Primary Endpoints

There are two primary endpoints for the study, one for Group A and one for Group B. Both primary endpoints must be achieved for the trial to be considered successful.

Primary endpoint for Group A:

Anesthesia Effectiveness: subject-reported pain score elicited by tympanic membrane tap following active lidocaine iontophoresis compared to sham lidocaine iontophoresis using the VAS.

Each Group A subject will each have a VAS score. If a subject in Group A discontinues iontophoresis prior to the TM tap assessment or declines the TM tap assessment, the subject will provide a pain score for the attempted procedure and will be included in the analysis of the primary endpoint. [REDACTED]

[REDACTED] Reasons for discontinuation will be documented and presented in the clinical study report.

Randomization will assign subjects to either unilateral active lidocaine iontophoresis or unilateral sham lidocaine iontophoresis treatment. Both the subject and the investigator

performing the taps will be blinded as to treatment assignment. Blinding is further described in **Sections 12.5.5 and 14.3.1**.

A single tap will be performed on the treated (or sham-treated) ear using a standardized dull otologic probe on the anterior part of the tympanic membrane. [REDACTED]

[REDACTED]

Primary endpoint for Group B:

Tube Placement Tolerability: Subject-reported pain score following TDS tube placement using the VAS.

Group B subjects will each have a single subject-level VAS score that reflects the pain associated with tube insertion; if both ears are treated the highest score of the two ears will serve as the subject-level score. The statistical test for the primary endpoint is a hypothesis test comparing mean VAS score to a performance goal of 4.5, as described in **Section 11.3**.

Group B subjects may require unilateral or bilateral tubes and will receive active lidocaine iontophoresis and tube placement using the TDS in each ear that requires a tube insertion.

[REDACTED]

- [REDACTED]
- [REDACTED]
- [REDACTED]
- [REDACTED]

The VAS score will be collected *after* any manipulations required to place the tube so that the pain score fully reflects the activities required to place the tube. A VAS score will be reported for each ear undergoing tube placement, and the highest (worst) pain reported by the subject will be used as the unit of analysis.

If a subject in Group B discontinues iontophoresis or tube placement, the subject will provide a VAS pain score for the attempted procedure. [REDACTED]

[REDACTED]

[REDACTED] Reasons for discontinuation will be documented and presented in the clinical study report.

11.9. Inclusion Criteria

Group A: At least one ear must meet ear-specific eligibility criteria.

Group B: Each ear indicated for tube placement must meet ear-specific eligibility criteria.

Group A:

1. Healthy adults, 18-50 years old at time of consent
2. Subject is able and willing to comply with the protocol and attend all study visits
3. Subject is able and willing to provide informed consent
4. Subjects with air conduction hearing thresholds of 25 dB HL or better at standard frequencies up to 2000 Hz, and 45 dB or better at 4000 Hz.
5. Subject is able to read and understand English

Group B:

1. Adults at least 18 years of age at time of consent
2. Indication for tympanostomy tube insertion per Clinical Practice Guideline,⁴⁰ or indicated for tympanostomy tube insertion due to barotrauma or Eustachian tube dysfunction per AAO-HNS Clinical Indicators⁴¹
3. Subject is able and willing to comply with the protocol and attend all study visits
4. Subject is able and willing to provide informed consent.
5. Subject is able to read and understand English.

11.10. Exclusion Criteria

Group A:

1. Pregnant or lactating females.
2. Prior ear iontophoresis procedure experience.
3. Subjects with conductive hearing loss.
4. Subjects with history of sensitivity or allergic reaction to lidocaine HCl, tetracaine, epinephrine, or any hypersensitivity to local anesthetics of the amide type, or any component* of the anesthetic drug formulation.

*Subjects with a known hypersensitivity to methylparaben and/or propylparaben (preservatives used in lidocaine HCl formulations), or to their metabolite para amino benzoic acid (PABA), or other components including potassium metabisulfite, sodium metabisulfite, ededate disodium or citric acid.

5. Familial history of insensitivity to lidocaine or other local anesthetics of the amide type.

6. Significantly atrophic, retracted, bimeric, monomeric or atelectatic tympanic membrane.
7. Perforated tympanic membrane.
8. Subjects with known history of ear surgery or TM condition that has the potential to affect the sensitivity of the TM (ex. prior tympanostomy tube insertion)
9. Otitis externa.
10. Damaged/denuded skin in the auditory canal.
11. Subjects with electrically sensitive support systems (pacemakers, defibrillators, etc.).
12. Cerumen impaction resulting in a significant amount of cleaning required to visualize the tympanic membrane.
13. Evidence of Otitis Media at day of procedure, or within the past three (3) months prior to procedure.
14. Other conditions that would preclude performing the study procedure including ear plug incompatibility.
15. Health conditions that, in the opinion of the investigator, would present undue risk to the subject, based on device/anesthetic drug product label warnings and precautions.

Group B:

1. Significantly atrophic, retracted or retraction pocket at location of tube placement, bimeric, monomeric or atelectatic tympanic membrane.
2. Perforated tympanic membrane.
3. Otitis externa.
4. Hemotympanum.
5. Damaged/denuded skin in the auditory canal.
6. Cerumen impaction resulting in a significant amount of cleaning required to visualize the tympanic membrane potentially causing abrasion or irritation to the external ear canal.
7. Notable ear discomfort experienced during audiologic or otoscopic examination.
8. Anatomy that precludes sufficient visualization of and access to the tympanic membrane.
9. Anatomy that necessitates tympanostomy tube placement in the posterior half of the tympanic membrane).

General Exclusion Criteria

10. Pregnant or lactating females.
11. History of sensitivity or allergic reaction to lidocaine HCl, tetracaine, epinephrine, or any hypersensitivity to local anesthetics of the amide type, or any component* of the anesthetic drug formulation.

*Subjects with a known hypersensitivity to methylparaben and/or propylparaben (preservatives used in lidocaine HCl formulations), or to their metabolite para amino benzoic acid (PABA), or other components including potassium metabisulfite, sodium metabisulfite, ededate disodium or citric acid.
12. Familial history of insensitivity to lidocaine or other local anesthetics of the amide type.
13. Electrically sensitive medical support systems (eg, pacemakers, defibrillators, cochlear implants)

14. Other conditions that would preclude performing the study procedure including iontophoresis system ear plug incompatibility.
15. Health conditions that, in the opinion of the investigator, would present undue risk to the subject, based on device/anesthetic drug product label warnings and precautions

If a previously-determined eligible subject presents on the procedure day with a change in condition, such as an acutely infected ear, the investigator may use clinical judgment to determine whether the condition as presented precludes performing the study procedure (Group B Exclusion 14). The physician also has the option to re-schedule the procedure if the condition is transient.

12.0 STUDY PROCEDURES

12.1. Investigator Training

Investigators will be asked to refer to the drug package insert, device Instructions For Use (IFU) and the Investigator's Brochure (CIB007001) for risks related to procedure, drug and device. The Investigators will be trained on use of the Iontophoresis and Tube Delivery Systems using a model system.

12.2. Evaluation Methods

12.2.1. Diagnosis (Group B)

Eligible subjects will be indicated for tympanostomy tube placement in alignment with the Clinical Practice Guideline.¹ The Clinical Practice Guideline for tympanostomy tubes in children was developed by a multidisciplinary panel, to provide clinicians with evidence-based recommendations on patient selection and surgical indications for and management of tympanostomy tubes in children.

In addition to indications aligned with the Clinical Practice Guideline for children, the adult subjects in Group B with barotrauma or Eustachian tube dysfunction may also be indicated for tube placement per AAO-HNS Clinical Indicators (2010).²Error! Bookmark not defined.

According to the Clinical Practice Guideline, the decision to perform unilateral or bilateral tympanostomy tube insertion when unilateral OME is present should be based on caregiver preference [to accept or decline the risk of a second surgical procedure] and the likelihood of persistent OME developing in the opposite ear. For AOM with presence of effusion, the Guideline recommends bilateral TT placement for unilateral or bilateral disease. With the current care paradigm, a physician may perform bilateral tube placement for a unilateral condition to avoid the risk of multiple OR procedures and general anesthesia exposures if the second ear becomes affected. Since this study procedure is conducted in-office, it is proposed that the decision to perform unilateral or bilateral TT placement for AOM with effusion be based on subject preference and physician clinical judgment regarding the likelihood of disease developing in the opposite ear, similar to the Guideline recommendation for chronic OME.

The indications for tube placement have been clarified (as noted in italics) in instances where unilateral placement may be deemed appropriate by the physician and acceptable by the subject. The clinical indications for tube placement for children include:

- Bilateral TT insertion for bilateral otitis media with effusion (OME) for 3 months or longer (chronic OME) and documented hearing difficulties;
- *Unilateral or bilateral* TT insertion for unilateral or bilateral OME, *respectively*, for 3 months or longer (chronic OME) and symptoms that are likely attributable to OME that include, but are not limited to, vestibular problems, poor school performance, behavioral problems, ear discomfort, or reduced quality of life;
- *Unilateral or bilateral* TT insertion for recurrent acute otitis media (AOM) with unilateral or bilateral middle ear effusion at the time of assessment for tube candidacy, where recurrent AOM is defined as three or more AOM episodes in the past 6 months or at least 4 AOM episodes in the past 12 months with at least 1 in the past 6 months.

In this study, the subject will be informed of the risk of subsequent OME or AOM in the contralateral ear and the potential need for a second tube insertion procedure should this occur. Prior to procedure, the Investigator must document which ears are intended for in-office tube placement.

12.2.2. Concomitant Medications

All prior and concomitant medications will be recorded. Prior medications will include all prescription and over-the-counter medications taken up to 28 days before procedure. All concomitant medications, and changes to medications, will be recorded during each subject's study enrollment period. Medications may be prescribed based on Investigator's discretion, except for drugs or devices under investigation through a different protocol.

12.2.3. Cranial Nerve Physical Exam

A standard cranial nerve physical exam will be employed at screening, post-procedure and at the follow-up visit to identify any potential adverse effects. [REDACTED]

[REDACTED]

[REDACTED] Any abnormalities will be recorded at screening and at the follow-up visit and the subject will be assessed for any adverse events. [REDACTED]

[REDACTED]

12.2.4. Otoscopy

An otoscopic exam will be conducted for both ears in all subjects for all study visits. The otoscopic examination will be used to visually examine the condition of the external ear canal and TM. Routine ear cleaning may be conducted only to the extent necessary to ensure the tympanic membrane and ear canal are free from matter that may interfere with iontophoretic delivery and to ensure visualization of the tympanic membrane.

The exam will be used to confirm eligibility and to assess the ear canal and TM for changes or adverse effects. Presence or absence of middle ear effusion will be assessed. In addition,

appearance of the myringotomy wound and patency of the tympanostomy tube (Group B only) will be evaluated at the follow-up visit. Tube functional patency will be determined through clinical assessments including otoscopic examination and tympanometry.

The screening otoscopic exam may be conducted up to 28 days prior to procedure and will be conducted for both ears of all subjects to determine eligibility and ears selected (Group A) or indicated (Group B) for treatment. Otosopic examination is considered standard of care for the Group B patient population and may be obtained prior to study informed consent as a screening assessment within 28 days prior to procedure. Otosopic images may be collected prior to and following iontophoresis.

12.2.5. Tympanometry

Standard tympanometry for both ears will be employed to assess TM function at screening (within 28 days prior to procedure) and at the follow-up visit for all subjects. Tympanometry data recorded will include tympanogram type, ear canal volume, peak pressure and static acoustic immittance and gradient as an objective measure of tube patency and middle ear status. If adequate tympanometer seal or a valid tympanogram cannot be achieved for screening tympanometry evaluation (eligible ears for Group A subjects and indicated ears for Group B subjects), the subject will be considered a screening failure, and will not be eligible for the study. Tympanometry is considered standard of care for the Group B patient population and may be obtained prior to study informed consent as a screening assessment within 28 days prior to procedure. Tympanostomy tube functional patency will be determined through clinical assessments including otoscopic examination and tympanometry.

12.2.6. Audiometry

Audiometry will be employed to evaluate hearing status and TM function for both ears at screening (within 28 days prior to procedure) and at the post-procedure follow-up visit for all subjects. Threshold testing will be conducted for each ear using air conduction and bone conduction at a minimum of 500, 1000, 2000 and 4000 Hz.

Audiometry is considered standard of care for the Group B patient population and may be obtained prior to study informed consent as a screening assessment within 28 days prior to procedure.

12.2.7. Anesthesia Effectiveness

Following iontophoresis for Group A, the Investigator will gently tap the TM once with a standardized dull otologic instrument. The tap will occur on the anterior half of the TM at the location where the tympanostomy tube would theoretically be placed. The Investigator will assess whether the TM is adequately anesthetized for a hypothetical tympanostomy tube placement based on subject response to the TM tap which is recorded via VAS. [REDACTED]

For Group B, the Investigator will inspect the ear canal and TM following iontophoresis and then lightly tap on the anterior half of the TM at the location where the tympanostomy

tube will be placed to elicit subject sensation which is recorded via VAS for each ear. [REDACTED]

[REDACTED]

The Investigator will assess whether the TM is adequately anesthetized for the tympanostomy tube placement based on subject response to the TM tap for each ear. This tap assessment method has been used successfully in prior studies to determine adequate anesthesia for subsequent tympanostomy tube placement for both children and adults.

12.2.8. Tolerability (VAS)

The Visual Analogue Scale (Figure 9) is an instrument for assessing procedural pain consisting of a 10cm line, where the ends of the line represent the extreme limits of pain intensity (“No pain” to “Worst possible pain”).⁴² The subject reports their pain intensity by making a mark along the line and the line is measured to convert the subject response to numeric score (0-10 in centimeters). The VAS is validated for use in subjects 8 years of age and older.³⁵ A standardized script will be read to the subject to ensure consistent interpretation of the pain rating task. [REDACTED]

[REDACTED]

[figure not shown]

Figure 9. Visual Analogue Scale (not shown to scale)

[REDACTED]

[REDACTED]

[REDACTED]

[REDACTED]

12.2.10. Vital Signs (Group B)

Vital signs (diastolic and systolic blood pressure, heart rate, respiratory rate and pulse oximetry) measurements will be used to evaluate baseline and peri-procedural vital signs to assess for any systemic effects of administered drug. Vital signs measurements will be recorded 15 minutes and immediately prior to iontophoresis, immediately following iontophoresis, following tube placement and at 30 and 60 minutes after completion of iontophoresis. Subjects who experience significant changes in vital signs (30% or greater compared to baseline) will undergo continued vital sign assessment until the vital sign measurements have returned to baseline (ie, beyond the 1-hour post-procedure evaluation period). Additionally, significant changes (30% or greater compared to baseline) will be considered adverse events.

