12.5. Procedure

12.5.1. Vital Signs (Group B)

Vital signs (diastolic and systolic blood pressure, heart rate, respiratory rate and pulse oximetry) will be monitored 15 minutes and immediately prior to iontophoresis, and again immediately following iontophoresis, following tube placement, 30 minutes and 60 minutes after completion of iontophoresis for all Group B subjects.

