12.5.10. Tympanostomy Tube Placement (Group B only)

In at least one ear, the Investigator will place the TT using the TDS while the subject’s head is gently stabilized by the clinic staff, as is typical for standard of care ear examinations. If the TT is not successfully placed by the TDS device, the investigator may choose to attempt tube placement with another TDS device. [REDACTED]

Following TDS tube placement, the subject will report their post-tube placement ear discomfort for each ear undergoing tube placement using the VAS. For bilateral tube placement subjects, the ‘worst’ ear pain score (highest score) will be used for analysis of the tube placement tolerability primary endpoint. [REDACTED]

[REDACTED] The subject’s VAS score for each ear following suction will be recorded. Post-operative care, including otic drops, will be prescribed per investigator’s discretion. All post-operative medications will be documented.

If an unexpected serious complication occurs during the procedure, the procedure will be terminated. The Investigator will take all appropriate intra- and post-treatment measures to ensure subject safety and proper treatment. The Investigator will notify Tusker Medical and their IRB immediately, but in no instances greater than 24 hours of the incident.

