12.7. Group B Follow-up

3-Week Post-Procedure Follow-Up Visit (+/- 7 Days)

1. All subjects are required to return for the 3-week post-procedure follow-up visit.
2. An otoscopic examination will be used to visually examine the condition of the external ear canal, TM, myringotomy wound and tube patency.

3. The subject will complete audiometry and tympanometry, and cranial nerve physical exam.
4. Subjects will be evaluated for any adverse events, and changes in concomitant medications will be recorded.
5. The subject will then be exited from the study

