13.0 ASSESSMENT OF SAFETY

13.1. Adverse Events

All reported or observed adverse events that occur during or after the procedure will be recorded. The study Investigator will determine whether an adverse event has occurred, whether life-threatening, serious or non-serious. Pre-existing conditions should not be reported as adverse events unless there has been a worsening in the severity or frequency,

which cannot be attributed to natural history or progression of the disease. This definition does not depend on the causal relationship with the device, drug or protocol requirements.

Any change of clinical significance, including vertigo, nausea and vomiting, derived from the protocol evaluations including observations and patient-reported findings will be included as adverse events. Changes in vital signs 30% or greater compared to baseline will be considered adverse events.

All Adverse Events (AEs) will be recorded on dedicated AE case report forms. The event, date of onset, severity, seriousness, duration, treatment, outcome, date or resolution and relationship to device, procedure or drug will be recorded on the AE case report form (CRF). AEs will be categorized by seriousness, relatedness to procedure, investigational drug, or device whether anticipated or unanticipated. All adverse events will be coded using standard terms.

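### The 30%-from-baseline vital-sign rule covers pulse oximetry, but from an assumed 94–100% baseline it fires only at a saturation of 65.8–70.0% or lower

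*Protocol*

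**What the plan says.** Protocol 12.2.10 lists the measurements and gives their purpose, which is to look for systemic effects of the drug: "Vital signs (diastolic and systolic blood pressure, heart rate, respiratory rate and pulse oximetry) measurements will be used". The trigger follows with no exception for any one sign: "Subjects who experience significant changes in vital signs (30% or greater compared to baseline) will undergo continued vital sign assessment". That assessment goes on past the one-hour period until the readings are back at baseline.

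The same threshold decides adverse-event status. Section 12.2.10 says "significant changes (30% or greater compared to baseline) will be considered adverse events", and Protocol 13.1 repeats it: "Changes in vital signs 30% or greater compared to baseline will be considered adverse events". SAP 14.2 names blood oxygen saturation among the vital signs and puts the 30% figure in brackets after its reference to clinically significant change. SAP 23.1 takes baseline as the last value before the procedure.

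In Protocol 12.5.1 the schedule ends with readings "following tube placement, 30 minutes and 60 minutes after completion of iontophoresis for all Group B subjects". Table 3 shows vitals at the procedure visit only. Among the 3-week assessments, Protocol 12.7 says "The subject will complete audiometry and tympanometry, and cranial nerve physical exam"; vital signs are not on the list.

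Protocol 13.1 also has a clause that does not depend on the 30%. Changes of clinical significance "derived from the protocol evaluations including observations and patient-reported findings will be included as adverse events".

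**The concern.** A relative change of 30% can be a workable limit for blood pressure or heart rate, which can move well away from baseline in either direction. Saturation cannot exceed 100% and normally sits near that ceiling. The same percentage therefore means something quite different for oximetry: the trigger falls far below levels that most clinicians would already want to watch.

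What is at stake is the monitoring rule itself. Section 12.2.10 contains the one written rule for extending vital-sign readings beyond 60 minutes. If a subject is still at 75–85% at that point, the oximetry reading alone does not meet it. Whether oximetry continues then depends on the judgement of the individual investigator, at up to 9 Group B sites. The automatic adverse-event flag has the same blind spot. The bracket in SAP 14.2 adds to it by inviting a reader to take 30% as the definition of clinical significance.

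**Working it through.** The 30% is a stated rule, not a derived figure, so there is no plan calculation to reproduce. The check is what the rule implies for saturation.

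**Inputs**
- Threshold: a change of 30% or more from baseline (Protocol 12.2.10 and 13.1, SAP 14.2).
- Measure: pulse oximetry, expressly included (Protocol 12.2.10, SAP 14.2).
- Baseline saturation: not given in the documents; assumed to be 94–100%.

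**Formulas**
- Relative reading: trigger = 0.70 × baseline.
- Percentage-point reading: trigger = baseline − 30.
- Relative fall to a reading x: (baseline − x) / baseline.

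**Where the rule fires**

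| Assumed baseline | Relative trigger | Percentage-point trigger |
|---|---|---|
| 94% | 0.70 × 94 = 65.8% | 94 − 30 = 64% |
| 98% | 0.70 × 98 = 68.6% | 98 − 30 = 68% |
| 100% | 0.70 × 100 = 70.0% | 100 − 30 = 70% |

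An upward change cannot fire it: 1.30 × 94 = 122.2% and 1.30 × 100 = 130.0%, which are impossible saturations.

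**What it misses**

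| Reading | Fall from 94% | Fall from 100% |
|---|---|---|
| 85% | 9/94 = 9.6% (9 points) | 15/100 = 15.0% (15 points) |
| 80% | 14/94 = 14.9% (14 points) | 20/100 = 20.0% (20 points) |
| 75% | 19/94 = 20.2% (19 points) | 25/100 = 25.0% (25 points) |

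None of these falls reaches 30 on either reading.

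**Contrast with another sign.** From an assumed heart rate of 70, the same rule fires at 0.70 × 70 = 49 and at 1.30 × 70 = 91. Both are attainable values, so the rule can act in both directions.

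**Readings scheduled after 60 minutes.** Protocol 12.5.1, Table 3 and Protocol 12.7 together give none. Beyond that point, oximetry under 12.2.10 depends on the trigger.

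**The suggested replacement (below 90%, or a fall of 5 or more points).** From 94% the floor fires first, at any reading below 90%. From 98% the fall criterion fires at 98 − 5 = 93%, and from 100% at 100 − 5 = 95%. Readings of 75–85% meet both parts from every assumed baseline.

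**The case against.** The strongest reply is that a subject at 75–85% would not be overlooked, and much of it stands.

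- **The rule works per subject, across five measurements.** A 30% change in systolic or diastolic pressure, heart rate or respiratory rate also starts continued assessment, which plausibly then includes oximetry. With assumed values, a respiratory rate that rises from 12 to 16 is a change of 4/12 = 33%. The gap is confined to marked desaturation in which no other sign moves that far.
- **Serious events must be followed.** Protocol 13.2 requires an unresolved serious event to be followed until it resolves, improves or stabilizes, and 13.3 lets a medically important event that puts the subject at risk count as serious. Persistent desaturation could be classed that way, and following it would in practice mean measuring saturation. This route depends on judgement and has no oximetry threshold.
- **General duties apply.** In an unexpected serious complication during the procedure, Protocol 12.5.10 says "The Investigator will take all appropriate intra- and post-treatment measures to ensure subject safety and proper treatment". Protocol 17.0 makes the investigator responsible for subject safety. Neither says at what saturation to act.
- **The data are reported.** SAP 14.2 gives the minimum saturation at each protocol-defined time point, and SAP 22.0 lists all case report form data by subject. A low value would be visible in the results, but that does not prompt a further reading on the day.
- **Some material cannot be seen.** Parts of the protocol are redacted, and the Group B risk analysis is in the Investigator's Brochure. A separate saturation limit there cannot be excluded. The readable text of 12.2.10 shows no redaction, however, and its rule expressly includes oximetry.

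A reader might infer that desaturations would go unrecorded as adverse events, or that desaturated subjects would be left unmonitored. The documents do not support either reading. The general clause in 13.1 still requires clinically significant changes to be recorded, and the provisions above make neglect unlikely.

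**Conclusion.** The point holds as a defect in one safety-monitoring rule. As written, the 30% threshold does not serve one of the five measurements that it names. From an assumed baseline of 94–100%, it fires on oximetry only at or below 65.8–70.0% (64–70% in percentage points). A reading of 75–85% at 60 minutes would not by itself start the continued assessment intended to pick up systemic drug effects. The offsets narrow the gap, but none gives sites a common oximetry trigger.

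The result rests on the assumed baseline range and on the visible text. The documents give no expected frequency of desaturation, so no number of affected subjects among the 30 in Group B can be claimed. Neither primary endpoint, its test nor its sample size is touched. The correction is worth making because it is cheap and bears on subject safety, not because the trial's conclusions depend on it.

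**What to change.** - In Protocol 12.2.10 and 13.1 and in SAP 14.2, limit the 30% rule to blood pressure, heart rate and respiratory rate.
- In the same three places, add an absolute oximetry criterion, used both for continued assessment and for automatic adverse-event status. As an assumed starting value, use a saturation below 90% or a fall of 5 or more percentage points from baseline. The medical monitor should confirm or replace this value before enrolment; it does not come from the documents.
- Reword the bracket in SAP 14.2 to match, so that 30% no longer reads as the definition of clinical significance for every sign.

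The cost is wording in three places. The scheduled oximetry readings already exist, so extra measurement arises only in subjects who meet the new criterion. The downside is a few more oximetry adverse events or extended observations, some of which may prove clinically unimportant.
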